2.3 DETERMINATION OF SAMPLE SIZE

A sample size of approximately 80 patients was selected based on the AE discontinuation rates after one year observed in the randomized Phase 3 pirfenidone studies and the randomized Phase 2 and 3 nintedanib studies (pirfenidone 14.6% AE discontinuation [Esbriet® US label 2014]; nintedanib 21% AE discontinuation [Ofev® US label 2014]). Given that for pirfenidone the discontinuation rate after 24 weeks was 6%-8% in studies PIPF-004 and PIPF-006 it is a reasonable assumption that the nintedanib discontinuation rate was around 10%-11%. As in this study of combination treatment, it is possible that the addition of nintedanib to ongoing pirfenidone treatment could increase the proportion of patients who discontinue because of an AE, given the overlap in the GI and hepatic effects of pirfenidone and nintedanib.

Assuming 85% of the patients complete 24 weeks of combination treatment, a sample size of 80 patients would be expected to yield an actual completion rate of 77.2% - 92.8% using a 95% confidence interval (CI). [Table 1](#) shows the 95% CIs associated with projected completion rates of 75%, 80%, 85%, 90% or 95%, assuming an 80-patient sample size.

Table 1 Confidence Limits for Sample Size Determination

Number of Patients who completed 24 weeks	Proportion of Patients who completed 24 weeks	Lower Bound of 95% CI	Upper Bound of 95% CI
76	95.0%	90.2%	99.8%
72	90.0%	84.4%	96.6%
68	85.0%	77.2%	92.8%
64	80.0%	71.2%	88.8%
60	75.0%	65.5%	84.5%

CI = confidence interval

Patients who are withdrawn from the study will not be replaced.

2.4 ANALYSIS TIMING

The following analyses will be performed for this study:

Table 2 Analysis Timing

Analysis	Timing of Analysis
First iDMC	When the first approximately 20 patients have completed 8 weeks of combination treatment or permanently discontinued study treatments
Second iDMC	When approximately 50% of the total patient group has completed 12 weeks of combination treatment or permanently discontinued study treatments
Third iDMC	When approximately 75% of the total patient group has completed 24 weeks of combination treatment or permanently discontinued study treatments
Final	All patients completed 24 weeks of combination treatment or permanently discontinued study treatments, and have performed the Follow-up visit.

3. STUDY CONDUCT

The study conduct is described in Section 2 (Study design).

3.1 RANDOMIZATION ISSUES

This will be an open-label trial involving only one treatment arm.

3.2 INDEPENDENT REVIEW FACILITY

Not applicable.

3.3 DATA MONITORING

An independent Data Monitoring Committee (iDMC) will review safety data and advise on study conduct at least three times during the study. For details on timing of the safety

**Pirfenidone and nintedanib — F. Hoffmann-La Roche Ltd
Statistical Analysis Plan MA29895, Version 2.0, final, 17 May 2017**

reviews please see Table 2 above. Efficacy data will only be provided if requested by the iDMC. For details please see Section 4.10.

4. STATISTICAL METHODS

This is a safety and tolerability study, not designed to assess efficacy, comprising only one treatment group. There are no formal statistical hypothesis tests to be performed, and there will be no adjustments for multiplicity of endpoints or within-subgroups comparisons. Efficacy analyses will be limited to descriptive statistics.

Categorical data will be summarized using frequencies and percentages (including a category for missing, if appropriate).

Continuous endpoints will be summarized using descriptive statistics (mean, standard deviation, minimum, 25th and 75th quartiles, median, and maximum).

Where data will be presented over time, e.g. Baseline, Week 12, Week 24, and early discontinuation visit, an end of treatment visit (EOT) will be added. This will include Week 24 data for patients who completed 24 weeks of combination treatment and data from the early discontinuation visit for patients who prematurely discontinued from combination treatment.

Other analysis methods will be specified below, where applicable. All data recorded in the electronic Case Report Form (eCRF), as well as derived data that will be used in analyses, will be listed.

Analyses will be presented for the total population, together with geographic region, i.e. US and non-US patients. Results for US and non-US will be presented as additional columns or additional blocks within the outputs of the total population.

Percentages will be based on the total population or on the number of patients in the respective geographic region, if not otherwise specified.

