4.1 ANALYSIS POPULATIONS

Only one analysis population, the Safety Population, has been defined as per CSP. No further analysis populations will be assessed.

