Hemoglobin A1c (HbA1c) was planned to be collected according to the initial version of the Clinical Study Protocol (CSP), but was removed in Amendment 3 of the CSP as not specifically relevant for this patient population. HbA1c values are continuously reported by the central laboratory, but will not be presented in any summary presentations. HbA1c values will only be listed.

**Pirfenidone and nintedanib — F. Hoffmann-La Roche Ltd
Statistical Analysis Plan MA29895, Version 2.0, final, 17 May 2017**

Clinical laboratory values will be presented separately for CTCAE-gradable and non-CTCAE gradable parameters by laboratory panel (hematology, serum chemistry).

Serum or urine pregnancy data will only be listed.

For laboratory analyses, visits will be assigned to visit windows as described in Section 4.9. This will also be valid for possible unscheduled visits. In case that multiple evaluable assessments occur within the same visit, the most extreme value will be used for analyses.

The following summaries will be prepared:

For each laboratory parameter, descriptive statistics of laboratory values at each scheduled visit (derived as described above), and absolute changes from baseline to post-baseline will be presented.

Shift tables presenting changes from baseline to worst CTCAE grade, in the indicated direction, will be provided for CTCAE-gradable parameters. These changes will also be expressed as shifts of 1 to 4 grades, 3 to 4 grades and 4 grades. If no CTCAE grade is available for a specific laboratory variable, shift tables will present worst changes with respect to normal range category (low, normal, high).

For CTCAE-gradable parameters, numbers and percentages of patients with laboratory values of Grade 3 and 4 will be presented over time. Further, the total number of visits with Grade 3/4 elevations, as well as the number and percentages of patients with Grade 3/4 elevations for each parameter will be provided.

Liver abnormalities (total bilirubin, alkaline phosphatase, ALAT (SGPT), ASAT (SGOT)) of Grade 3 and 4 will be presented showing numbers and percentages of patients for each parameter separately, as well as in combination with at least one of the other parameters elevated post-baseline. Line graphs will also be provided.

All laboratory data will be listed.

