4.7.8 ECG

QTcF values will be assigned to the following intervals: < 500 ms, 500–550 ms, and > 550 ms. Numbers and proportions of patients with their maximum QTcF interval category will be summarized at Baseline, Week 24 or early discontinuation, EOT and Follow-up. Absolute changes from the Baseline to each post-baseline visit in QTcF values will be categorized to ≤ 30 ms, 31–60 ms, and > 60 ms. Numbers and proportions of patients in each category will be presented for each post-baseline visit. Planned visits will be used for presentations.

At each visit, the ECG result is to be assessed as being normal, abnormal - not clinically significant, abnormal - clinically significant, or unable to evaluate. Changes from baseline to each post-baseline visit will be presented showing numbers and proportions of patients in each combination of categories.

Descriptive statistics for heart rate and changes from baseline for each visit will be presented.

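### By-visit laboratory (and some ECG) percentages default to the whole Safety Population, so patients no longer assessed dilute them

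*SAP*

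**What the plan says.** Section 4 (Statistical Methods) gives a general rule for every table: "Percentages will be based on the total population or on the number of patients in the respective geographic region, if not otherwise specified". Section 4.1 adds that "Only one analysis population, the Safety Population, has been defined as per CSP", so the total population means everyone treated. Version 1.0 has the same default.

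The by-visit outputs that fall under this rule are:

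- **Laboratory (4.7.6):** for CTCAE-gradable parameters, "numbers and percentages of patients with laboratory values of Grade 3 and 4 will be presented over time".
- **ECG (4.7.8), QTcF change categories:** "Numbers and proportions of patients in each category will be presented for each post-baseline visit". Changes in the normal/abnormal reading are also shown for each post-baseline visit.
- **ECG (4.7.8), maximum QTcF category:** these "will be summarized at Baseline, Week 24 or early discontinuation, EOT and Follow-up".

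Neither section states its own denominator, and neither does Section 4.9 on visit windows. Table 5 in Section 4.9 lists early discontinuation as an analysis visit separate from Week 24 and EOT.

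On attrition, Section 2.3 plans with "Assuming 85% of the patients complete 24 weeks of combination treatment" and states that "Patients who are withdrawn from the study will not be replaced". Under the synopsis (Appendix 1), a patient who stops has an early discontinuation visit and a follow-up visit and then leaves the study. Section 4.8 provides no imputation for laboratory or ECG values. Section 4 allows a category for missing values, but only as an option.

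**The concern.** A by-visit percentage is normally read as the share of the patients examined at that visit who had the finding. Under the default it is the share of all patients ever treated. The two agree while everyone is still assessed. They separate as patients leave, because the divisor stays fixed while only those who attend can enter the numerator.

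The consequence is a drift that has nothing to do with the drugs. If the true rate among assessed patients were constant over time, the printed percentage would still fall from visit to visit. In a study whose purpose is safety and tolerability, a reader could take that fall for an abnormality becoming less common. The early discontinuation visit is the extreme case: only patients who stopped attend it, yet the default divides by everyone.

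**Working it through.** **Inputs.** N = 80 (Section 2.3: "A sample size of approximately 80 patients was selected"). Completers m = 76, 72, 68, 64 or 60 (Table 1), with 68 the planning value. Two assumptions are needed: the patients assessed at Week 24 are the completers, and the event counts e are illustrative because the SAP gives none.

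**The plan's own figure.** For 68 of 80, 0.85 ± 1.96 × √(0.85 × 0.15 / 80) = 0.85 ± 0.078, that is 77.2% to 92.8%. This matches Table 1. The SAP prints no by-visit percentage to reproduce, so only the counts in Table 1 are used below.

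**Dilution at Week 24.** The default prints e/N. The percentage among patients assessed is e/m. Their ratio is m/N, whatever e is, and since m ≤ N the printed figure can never be the larger. With e = 4:

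| Assessed, m | Default, 4/80 | Among assessed, 4/m | Ratio m/N | Relative shortfall |
|---|---|---|---|---|
| 76 | 5.0% | 5.3% | 0.95 | 5% |
| 72 | 5.0% | 5.6% | 0.90 | 10% |
| **68** | **5.0%** | **5.9%** | **0.85** | **15%** |
| 64 | 5.0% | 6.3% | 0.80 | 20% |
| 60 | 5.0% | 6.7% | 0.75 | 25% |

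In absolute terms the gap runs from 0.1 percentage points (2 events, m = 76: 2.5% against 2.6%) to 2.5 points (6 events, m = 60: 7.5% against 10.0%).

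**Effect on a time course.** Suppose 5% of assessed patients have the abnormality at every visit. With all 80 assessed the default prints 5.0%. With 68 assessed it prints 0.05 × 68 / 80 = 4.25%. The fall is due to attrition alone.

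**Early discontinuation as its own row.** With 68 completers, at most 80 − 68 = 12 patients attend. With an illustrative 3 events the default prints 3/80 = 3.8% and the percentage among attenders is 3/12 = 25%; the ratio is 12/80 = 0.15. Over Table 1 the number of attenders would be 4 to 20, so the ratio would be 0.05 to 0.25.

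**Tables that are not diluted.** EOT combines Week 24 data for completers with early discontinuation data for the rest. If all attend, 68 + 12 = 80 patients are assessed and the ratio is 1. The same holds for the maximum-QTcF table at Week 24 or early discontinuation. Follow-up is scheduled for both completers and discontinuers, so it is diluted only by visits that are missed.

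**The case against.** Four points on the other side have weight.

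- **The toxicity message is carried elsewhere.** The SAP plans an EOT visit, shifts to worst CTCAE grade, the percentage of patients with any Grade 3/4 elevation per parameter, and Grade 3/4 liver abnormalities singly and in combination. The Safety Population is the right denominator for the ever-event summaries. This stands. A reader might infer that the plan understates toxicity overall or loses the events of patients who stop. The documents do not support that: those events reach the EOT and worst-value tables, and all laboratory data are listed.
- **ECG is mostly spared.** The schedule in Appendix 2 has post-baseline ECGs only at Week 24, early discontinuation and Follow-up, so there is no QTcF time course to distort. This also stands. What remains exposed is the change-category and normal/abnormal tables if shown separately by visit, and Follow-up where patients miss it.
- **Absent patients are not counted as normal.** It is tempting to say that they are, but counts accompany the percentages, a missing category may be shown and nothing is imputed. The share of treated patients with an abnormality seen at a visit is also a legitimate quantity. However, the missing category is optional and would leave the printed percentage unchanged, and the SAP does not require the number assessed to be shown.
- **Another denominator does not cure selective dropout.** A patient who stops for toxicity leaves both numerator and denominator when only assessed patients are counted. This is correct, and it limits what the fix can claim.

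The analyses are also descriptive, and the primary outcome, the AE-discontinuation proportion and TEAE incidence do not depend on this rule.

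**Conclusion.** The point holds for by-visit laboratory Grade 3/4 percentages and for the few per-visit ECG tables. It is a stated rule that gives diluted percentages, not a detail left open. At the planned completion rate the Week 24 figures are 15% lower in relative terms than among patients assessed (5% to 25% over Table 1), which is under one percentage point for four events. The effect is large only if early discontinuation is tabulated as its own row, which Table 5 allows but does not make certain.

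The direction follows from m ≤ N. The size rests on taking the completers as the patients assessed at Week 24, on all 12 non-completers attending the early discontinuation visit, and on illustrative event counts. The same dilution applies within the US and non-US columns, but the SAP gives no planned regional numbers from which to size it. The overall, worst-grade and EOT safety summaries remain sound.

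**What to change.** Add one rule to Section 4, along these lines:

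*In by-visit laboratory and ECG summaries, percentages use as denominator the patients with a non-missing assessment at that visit; for changes and by-visit shifts, a non-missing baseline is also required. This n is shown beside N in each column. Overall incidence, worst post-baseline and ever-event summaries use the Safety Population.*

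Apply the rule to the regional columns and to the early discontinuation row if there is one. Add a table note that the by-visit percentages describe the patients still assessed and should be read with the EOT and worst-grade summaries, because the new denominator removes dilution by unassessed patients but not bias from toxicity-driven dropout.

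The cost is a short SAP amendment and a change to the table shells. No new data are needed. Some by-visit percentages will be somewhat higher than under the current rule.

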4.1 ANALYSIS POPULATIONS

Only one analysis population, the Safety Population, has been defined as per CSP. No further analysis populations will be assessed.

4.1.1 Full Analysis Set

Not applicable.

4.1.2 Per Protocol Population

Not applicable.

4.1.3 Pharmacokinetic-Evaluable Population

Not applicable.

4.1.4 Safety Population

The Safety Population will consist of all patients who received at least one dose of nintedanib or pirfenidone on or after the Baseline visit.

Analyses will be produced for the Safety Population, if not otherwise specified.

4.2 TRIAL PERIODS, OBSERVATION AND ANALYSIS TIMES

In case that durations are to be calculated (e.g. treatment duration), these will be derived based on days and converted to months and years if needed, using 30.4375 and 365.25, respectively, as denominator if not otherwise specified.

4.2.1 Study Days

Study day is defined as the number of days since combination treatment start date, and is calculated as:

- For assessments on or after the day of start of combination treatment:
Study day = Assessment date – Date of start of combination treatment + 1.
- For assessments before the day of start of combination treatment:
Study day = Assessment date – Date of start of combination treatment

The day of the first dose of combination treatment is defined as Day 1.

4.2.2 Baseline and Screening Observations

Table 3 Definition of Baseline and Screening Observations

	Definition
Combination Treatment Start Date	Combination Treatment Start Date is the date of first administration of nintedanib and pirfenidone on or after the Baseline visit. Combination treatment start date will be used for all safety assessments and for the calculation of study days.
Baseline data	Baseline is defined as the last valid assessment prior to start of combination treatment. This may not be the same as the Baseline visit as per eCRF. Generally, it is assumed that measurements referring to the Baseline visit have been performed before study drug was given. This applies

**Pirfenidone and nintedanib — F. Hoffmann-La Roche Ltd
Statistical Analysis Plan MA29895, Version 2.0, final, 17 May 2017**

	
for laboratory values, vital signs, ECG, pulmonary function tests and [REDACTED]
 
Adverse events occurring on the combination treatment start date will not be considered baseline, but treatment-emergent.

Screening data	
Screening measurements are all the measurements performed before the combination treatment start date and not respecting the “baseline” criteria.

4.2.3 On-treatment Assessments

On-treatment assessments will be the assessments performed on or after the combination treatment start date until the date of the Follow-up visit, which is planned to be performed 28 - 35 days after the date the subject discontinued from/completed combination treatment (see Section 4.2.5 for details).

However, treatment emergent adverse events are defined as adverse events with an onset date on or after the day of initiation of combination treatment up to 28 days after the date subject completed or early discontinued from combination treatment period as per eCRF (eCRF form Study Drug Completion/Early discontinuation).

4.2.4 Post-treatment Assessments

Post-treatment evaluations will be the evaluations performed later than the Follow-up visit. Post-treatment evaluations are not expected to occur. If there should be any, the data of assessments falling into this time-window will only be listed.

In addition adverse events, reporting more than 28 days after early discontinuation/completion of combination treatment will be considered as post-treatment.

4.2.5 Treatment Start and Stop Dates

As this is a combination treatment study, different assessments with respect to study treatment are possible: Pirfenidone alone, nintedanib alone, and combination treatment. To account for this, the following definitions will be made:

Table 4 Definition of Treatment/Combination Treatment Start and Stop Dates

	Treatment start date	Treatment end date
Combination treatment	Date of first administration of nintedanib and pirfenidone on or after the Baseline visit = Start date of combination treatment	Date subject completed or early discontinued from combination treatment period as per eCRF (eCRF form Study Drug Completion/Early discontinuation). = Date of completion or discontinuation from combination treatment
Pirfenidone	Start date of combination treatment	Date of last administration of pirfenidone as recorded in the study drug log for pirfenidone, until the date of completion or discontinuation from combination treatment.
Nintedanib	Start date of combination treatment	Date of last administration of nintedanib as recorded in the study drug log for nintedanib, until the date of completion or discontinuation from combination treatment.

4.2.6 Cut-off points

Clinical cut-off for final analysis is defined as the date of last patient last visit (LPLV). A description of data cleaning activities and a date for database lock will be provided by Data Management in a separate document.

4.3 ANALYSIS OF TREATMENT GROUP COMPARABILITY

This is an open-label single arm phase IV study that will assess the combination treatment of pirfenidone and nintedanib. Consequently, no formal assessment of treatment group comparability can be conducted.

4.4 ANALYSIS OF STUDY CONDUCT

4.4.1 Patient Disposition

An overview on patient disposition, showing number and percentages of patients screened (as per IxRS), enrolled, treated and completed the study will be provided. For patients who have early discontinued study treatment or the study, frequencies of reasons for early discontinuation will be provided. Patients enrolled are all patients that have signed informed consent and are entered into the clinical database.

For further safety-related disposition analyses please see Section [4.7.1](#).

An overview on patients' enrolment by country and center will be provided.

4.4.2 Major Protocol Deviations

A Per-Protocol population will not be defined; however, major protocol deviations and eligibility violations will be summarized by frequency tables and all patients with protocol deviations will be listed.

Protocol deviations will be collected in PDMS, reviewed by the medical monitors, and will be provided in a SAS dataset via the Biometrics Computing Environment (BCE). All deviations provided in that spreadsheet will be considered as major protocol deviations.

4.4.3 Demographic and Baseline Characteristics

Baseline and disease characteristics such as demographics, medical history, tobacco and substance use history will be summarized by descriptive statistics or frequency tables.

Demographics

The following demographic characteristics will be summarized:

- Age (years): as entered in the eCRF at the screening visit
- Age categories: 18 – 64 years, 65 - 84 years, ≥85 years
- Gender (male/female)
- Race: White, American Indian or Alaska Native, Asian (Indian subcontinent, Other than Indian subcontinent), Black or African American, Native Hawaiian or Other Pacific Islander, Unknown. In case that more than one race will be ticked, a concatenated variable, containing all races will be presented (e.g. Asian/White).
- Ethnicity: Hispanic (Latino), Non-Hispanic (Non-Latino)
- Weight (kg) at baseline
- Height (cm) at baseline

- BMI (kg/m²) at baseline. BMI will be calculated as weight in kg / (height in cm)² × 10000

Data on female reproductive status will be presented descriptively; methods of contraception will only be listed.

Tobacco use history and substance use

The history of tobacco use will be summarized with the following characteristics:

- Tobacco use history (never, current, previous)
- Pack-years, smokers only

Numbers and percentages of patients for following characteristics will be presented to specify substance use:

- Current substance use (yes/no)
- Substance use (cannabinoids, amphetamines, opiates, caffeine, benzodiazepines, barbiturates, cocaine)

Medical History

Medical history will be coded using the Medical Dictionary for Regulatory Activities (MedDRA®), version 19.0 or higher and will be summarized presenting numbers and frequencies by primary System Organ Class (SOC) and Preferred Term (PT). If patients have more than one disease within a SOC or PT they will be counted only once for the respective SOC or PT.

Historical Pulmonary Function Test

The number and percentage of patients who performed the respective pulmonary function test (FVC, DLco, FEV₁, and FEV₁/FVC ratio (calculated)) in the past will be provided. This assessment was planned to be performed closest to 6 months before the Screening visit. These historical pulmonary function test parameters will be summarized using descriptive statistics. Both, absolute and percent predicted values will be presented. The time from assessment of the historical value to Screening will be summarized and defined as follows:

Time from assessment to Screening = (Date of Screening – Date of historical assessment) + 1.

Previous Pirfenidone Treatment

The number and percentage of patients with previous pirfenidone treatment and the duration of previous pirfenidone treatment will be summarized descriptively.

**Pirfenidone and nintedanib — F. Hoffmann-La Roche Ltd
Statistical Analysis Plan MA29895, Version 2.0, final, 17 May 2017**

[Redacted text block]

